Patients will be participating in the study for the duration of their surgery and for 24 hours after induction.

We anticipated it to take 1 year to enroll all study subjects.

We anticipate an extra 12 months after completion of the study for the investigators to complete the primary analyses.

6) Study Endpoints

The primary endpoints include:

- 1. Blood pressure changes during induction
- 2. Heart rate changes during induction

The secondary endpoints include:

- 1. Pain at injection
- 2. Myoclonic movements
- 3. PONV in PACU
- 4. Postoperative pain score
- 5. Incidence of adverse reactions during induction
- 6. Severity of adverse reactions during induction

7. Dose and frequency of vasoactive agents and other concomitant medications used to treat adverse reactions of propofol / etomidate

8. Sedation depth using bispectral index (BIS)

- 9. Eyelash reflex disappear time
- 10. Intubation time
- 11. Dose and frequency of analgesic and other sedatives used

7) **Procedures Involved**

This is a non-blinded, randomized, parallel-group study in patients scheduled for elective surgery under general anesthesia and orotracheal intubation to compare etomidate plus propofol vs. propofol or etomidate alone on induction of anesthesia.

There will be three cohorts of 25 patients per cohort with one cohort administered propofol, one cohort administered etomidate, and one cohort administered propofol

etomidate. The sample size was calculated with the blood pressure change \pm 20 mmHg, SD \pm 25 mmHg, power of 0.80 and p value of 0.05 and resulted 25 in each group.

The research team will create 75 envelopes. Each will be numbered, 25 will be in propofol group, 25 will be in etomidate group and 25 will be in propofol/etomidate group. On the day of surgery, one envelope will be randomly picked for each participant.

Patients in the three cohorts will be administered a 30 second bolus by manual hand push.

Intensive PD and safety assessments will be performed prior to dosing on Day 1 until 24 hours post-dose (Day 2). There are no plans for long-term follow-up past the 24 hours.

Three cohorts are as follow:

- 1. Propofol group: 2 mg/kg propofol
- 2. Etomidate group: 0.3 mg/kg etomidate
- 3. Propofol plus etomidate group: 1mg/kg propofol plus 0.15mg/kg etomidate.

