Systolic blood pressure, diastolic blood pressure, mean arterial pressure, heart rate will be monitored and recorded before induction, at induction and intubation followed by 1, 3, 5 and 10 minutes after intubation.

Pain on injection will be measured using 4 graded scale; 0 --- no pain, 1 --- verbal complaint of pain, 2 --- withdrawal of arm, 3 --- both verbal complaint and withdrawal of arm.

The incidence and degree of myoclonic movements also recorded as follows: 0 = no myoclonic movements, 1 = minor myoclonic movements, 2 = moderate myoclonic movements, 3 = major myoclonic movements.

The medications used in the 3 groups are clinically used already with FDA approval for their use. This is an observational study and we will compare the effects of the three groups with their medication uses on the parameters we listed above: systolic blood pressure, diastolic blood pressure, mean arterial pressure, heart rate, pain on injection, myoclonic movements, PONV and BIS numbers.

Non-English speaking participants are still eligible for the study. We will use translation services in line with HRP 090 and HRP 091 and the consent short form to enroll interested non-English speaking participants. If we find that we have enrolled 2 patients of a particular language using the short form as the study progressed, we will obtain full translation of the consent form into that language through the use of UCD Translation Services.

8) Data and/or Specimen Management and Confidentiality

All data will be summarized using descriptive statistics. Summaries of continuous variables will present mean, median, standard deviation, minimum, and maximum; summaries of categorical variables will present frequencies and percentages. All data will be presented in subject data listings.

Subject enrollment and disposition, including reasons for early withdrawal from the study, will summarized by group.

Demographic variables will be summarized by group for all enrolled subjects. Data will be stored up to 3 years after finishing the study.

This is a pilot study with a proposal to enroll 25 patients into each group for a total of 75 patients randomized.

We expect to complete data analysis on 20 patients in each group for a total of 60 patients due to patient withdrawal either voluntarily or due to formal withdrawal criteria, ie difficulty with securing patient airway.

9) Provisions to Monitor the Data to Ensure the Safety of Subjects

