Title: Comparison of Etomidate Plus Propofol, Etomidate Alone on Induction of Anesthesia

NCT03820388

Document Date: September 26, 2017

Statistical Analysis

Sample size calculations were based on our pilot study, and we found MAP to be 80.1 (± 10.3) mmHg, 90.3 (± 10.4) mmHg, 91.0 (± 11.6) mmHg in group P, PE and E at induction. Using PASS 15.0 software, a sample size of 20 patients per group would be needed to detect statistically significant differences with the power of 0.9 and the alpha level of 0.05. Considering a possible 20% dropout rate, 25 patients per group were recruited for the study.

Parametric values were expressed as mean (SD), or percentages of the total number of patients (%). Categorical data were analyzed using χ^2 or Fisher's exact test as appropriate. The hemodynamic parameters among the three groups were compared using the general linear model (GLM). We also considered time of evaluation as a within-subject factor, and the intervention state as a between-subject factor. The time groups (interaction terms) were considered group differences among the three groups in their responses over time. We used Mauchly's sphericity test for compound symmetry assumption. Differences in hemodynamic variables between the three groups at different time points were compared by post hoc Bonferroni test. $P < 0.05$ was considered statistically significant. All statistical analyses were performed with SPSS 22.0 (SPSS; Chicago, IL, USA).

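### The protocol's 25 per group has no allowance for loss, yet 20 are expected to be analysed; on a two-sided reading power there is about 0.70, not 0.80, and the SAP reaches 25 by another route

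*Protocol*

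**What the plan says.** **Protocol, section 7 (Procedures Involved).** The inputs are "blood pressure change \pm 20 mmHg, SD \pm 25 mmHg", with "power of 0.80 and p value of 0.05 and resulted 25 in each group". The section does not name the pressure variable (systolic, diastolic or mean), the time point, the test or the sidedness. It does not say whether 25 is the number enrolled or the number evaluable, and it mentions no adjustment for dropout.

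**Protocol, section 8 (Data and/or Specimen Management and Confidentiality).** Enrolment equals the calculated number: "This is a pilot study with a proposal to enroll 25 patients into each group for a total of 75 patients randomized". The same section then anticipates withdrawals: "We expect to complete data analysis on 20 patients in each group for a total of 60 patients".

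**SAP, Statistical Analysis.** The basis here is pilot mean arterial pressure (MAP) at induction: 80.1 (SD 10.3), 90.3 (10.4) and 91.0 (11.6) mmHg in the propofol, combination and etomidate groups. From these, "a sample size of 20 patients per group would be needed to detect statistically significant differences with the power of 0.9" at alpha 0.05. The step to 25 is then "Considering a possible 20% dropout rate, 25 patients per group were recruited for the study".

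**The concern.** In the protocol, 25 is the output of the power calculation. In the SAP, 20 is the output and 25 is that number after inflation for dropout. If the protocol's 25 is the number needed for analysis, a trial that randomises 25 and expects to lose a fifth of them does not have the power it states.

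The two calculations also differ in the variable (an unspecified pressure change against MAP at induction), the SD (25 against roughly 10 to 12 mmHg) and the power (0.80 against 0.90). Neither document says which one governs. Blood pressure change during induction is a primary endpoint, and the protocol records three pressures at several time points. The planning assumptions therefore matter to anyone judging what a null result would mean.

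**Working it through.** **Inputs.** Protocol section 7: difference 20 mmHg, SD 25 mmHg, so d = 20/25 = 0.80; power 0.80; alpha 0.05. Protocol section 8: 25 randomised and 20 analysed per group, a loss of 5/25 = 20%. Assumption, because the protocol is silent: a two-sided comparison of two group means.

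**1. Reproduce the protocol's 25.**
n = 2(z₀.₉₇₅ + z₀.₈₀)²/d² = 2(1.960 + 0.842)²/0.64 = 24.53 (unrounded quantiles), so 25 per group. The exact t-test gives 25.52, so 26. The stated inputs use all 25 patients.

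**2. Power at the numbers randomised and analysed.** Normal approximation: power = Φ(d√(n/2) − 1.960).
- n = 25: Φ(2.828 − 1.960) = Φ(0.868) = 0.807
- n = 20: Φ(2.530 − 1.960) = Φ(0.570) = 0.716

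| Analysed per group | Normal | t-test |
|---|---|---|
| 25 | 0.807 | 0.791 |
| 20 | 0.716 | 0.693 |

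**3. Detectable difference at 20 per group, 80% power.** 25 × (1.960 + 0.842) × √(2/20) = 22.15 mmHg (normal); 22.73 mmHg (t).

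**4. Enrolment needed to keep 25 for analysis after 20% loss.** 25/0.8 = 31.25, so 32 per group. Starting from the t-test's 26: 26/0.8 = 32.5, so 33.

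**5. Other readings of the protocol's inputs.**
- One-sided 0.05: n = 2(1.645 + 0.842)²/0.64 = 19.3 (normal) or 20.03 (t). Inflated, 20/0.8 = 25. Power at 20 is 0.812 (normal) or 0.799 (t). This fits both 25 and 20.
- One-way ANOVA with one group 20 mmHg from the other two: n = 24; power at 20 is 0.723. The shortfall is the same as in step 2.
- One-way ANOVA with means spaced 0/10/20: n = 32. With means −20/0/+20: n = 9. Neither gives 25.
- Two-sided with Bonferroni adjustment for three pairs: n = 33 (normal) or 35 (t). Neither gives 25.

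**6. Check the SAP's own calculation.** Pooled SD = √((10.3² + 10.4² + 11.6²)/3) = √116.27 = 10.78. The grand mean is 87.13 and the squared deviations of the three means sum to 74.45. The one-way ANOVA noncentrality at 20 per group is 20 × 74.45/116.27 = 12.81, giving power 0.887. At 21 per group power is 0.903. Inflation: 20/0.8 = 25. The SAP's 20 and 0.9 therefore hold to within one patient per group.

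**The case against.** **The shortfall rests on an assumed sidedness.** A one-sided 0.05 test needs about 20 per group, and 20/0.8 = 25, so both protocol numbers are recovered at the stated power. The hemodynamic hypotheses in protocol section 2 are directional. This reading cannot be excluded. However, section 7 states neither a one-sided test nor an inflation step, it writes the change with a plus-or-minus sign, and the hypotheses cover both hypotension and hypertension. Two-sided is the natural reading. If one-sided was meant, the protocol leaves out the two steps on which its 0.80 depends.

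**The later SAP already gives a fuller calculation.** It names the variable, the time point, the SDs with their source, the power and the dropout rate, and it roughly reproduces. A reader could fairly treat it as governing. That stands, and it means that 0.69 to 0.72 should not be read as the trial's power on the SAP's basis: with SDs of 10 to 12 mmHg, a 20 mmHg difference in MAP at 20 per group would have power above 0.99. But the SAP does not say that it replaces the protocol's figure, and it too leaves the test and sidedness of its calculation unstated.

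**This is a pilot study.** That lowers the stakes. The protocol nonetheless states hypotheses and a power, and the power should be true at the number it expects to analyse.

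**Conclusion.** The concern holds as a conditional statement. With a two-sided 0.05 comparison of two means and the protocol's inputs, 25 is the uninflated requirement. At the protocol's own expected 20 per group, power is 0.69 (t) to 0.72 (normal) against the stated 0.80, and the difference detectable with 80% power is about 22 to 23 mmHg. Sidedness decides the size of the shortfall: under a one-sided test, power at 20 is about 0.80 and the shortfall disappears.

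The inconsistency does not depend on sidedness. Section 7 presents 25 as the calculated result and the SAP presents it as a dropout-inflated number, on different variables, SDs and powers, with nothing to connect them. This does not show that the trial is underpowered on the SAP's inputs. It should be fixed; confidence is medium because the test and sidedness are unstated.

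**What to change.** Two routes are open.

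1. **Withdraw the protocol's calculation and keep a single one in both documents.** It should name the pressure variable, time point, test and sidedness, give the SD with its source, and state power at 20 analysed per group. If the SAP's basis is kept, one-way ANOVA power at 20 is about 0.89.
2. **Restate the protocol's figure.** If the test is confirmed as two-sided, suitable text is: 25 randomised and about 20 analysed per group; two-sided alpha 0.05; power about 0.69 to 0.72 for a 20 mmHg difference with SD 25 mmHg (80% power for about 22 to 23 mmHg). The SAP should then say how its own calculation relates to this one.

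If a one-sided test with inflation was intended, say so and show both steps: 20 needed, then 20/0.8 = 25.

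The cost is wording in the protocol, and in the SAP if one calculation is kept. No patients are added, and neither conduct nor analysis changes. Under the second route the protocol's stated power becomes less favourable.

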As this is a minimal risk study, there are no plans to monitor the data.

10) Withdrawal of Subjects

The PI and research team can withdraw subjects from the study without their consent if difficulty securing their airway is encountered.

11) Risks to Subjects

The potential risks are breack to confidentiality and risks associated with the study drugs, Propofol and Etomidate.

In order to safeguard our patient's confidential data and to lessen the likelihood of a breach of confidentiality, the following parameters will be put in place:

- 1. The data will be stored in the PI's password-protected computer in his locked office.
- 2. We don't anticipate needing to transport any data, but if need be, the data will be transported via a hospital issued, password protected IRONKEY.
- 3. Patients' names and medical record numbers will be used initially. A numerical number (0001 to 0050) will be assigned to each patient.

- 4. If the data need to be transmitted, the UCD secured email system will be used and the receiving end needs to be same secured email system.
- 5. Only the research team members can access the data.

Risks associated with Propofol and Etomidate :

Risk of Etomidate:

Transient venous pain on injection

Transient Skeletal muscle movements

Respiratory System: Hyperventilation, hypoventilation, apnea of short duration, laryngospasm, hiccup and snoring suggestive of upper airway obstruction.

Circulatory System: Hypertension, Hypotension, tachycardia, bradycardia, arrhythmias

Risks of Propofol:

Cardiovascular: Bradycardia, arrhythmia, tachycardia, hypotension, decreased cardiac output

Central nervous system: movement

Metabolic/Nutritional: Hyperlipemia

Respiratory: Apnea, respiratory acidosis during weaning

Skin and appendages: Rash, pruritus

12) Potential Benefits to Subjects

Both propofol and etomidate are used in everyday clinical practice. There are still controversial over which out of the two is better. By using the combination of etomidate and propofol at a reduced dosage in cohort 3, we hope that patients can benefit from those drugs through the minimization of side effects.

We are unable to tell if there will be a direct benefit to the study participant.

13) Multi-Site Research

N/A

14) Community-Based Participatory Research

N/A

15) Sharing of Results with Subjects

There are no plans to share study results with participants.

16) Prior Approvals

N/A

17) Provisions to Protect the Privacy Interests of Subjects

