Eligible patients will be screened through electronic medical record review up to 48 hours before their scheduled elective surgery. Patients will be approached on the day of the surgery in the UC Davis preoperative holding area of the main hospital to gauge for study interest. Research team will obtain consent from interested participants and honor any withdrawal requests based off of randomization group or time-constraints.

This observational study does not allow for any interventions nor study procedures outside of the patient's normal care, so we will limit unnecessary interactions with the patients to minimize the sense of intrusiveness a subject might experience in response to standard questions, examinations, and procedures.

The research team will complete the HIPPA and required CITI training. Only at the time of data collection can the research team access the necessary patient's information.

18) Compensation for Research-Related Injury

There is no compensation for participating in this minimal risk study.

19) Economic Burden to Subjects

Both medications are already routinely ordered and administered, and will be billed accordingly to the patient's insurance.

20) Drugs or Devices

This is an observational study using FDA-approved medications that are used in everyday practice for anesthesia induction purpose.

Medication is routinely stored in PYXIS and will be taken by the anesthesiology.

21) ClinicalTrials.gov Registration

Section 1: NIH Funded Studies

If yes to BOTH, the study must be registered on Clinicaltrials.gov.

Yes	
	This study is funded by the NIH . (If this study is not funded by NIH, go to
	Section 2.)
	One or more human subjects will be prospectively assigned to one or more
	interventions (which may include placebo or other control) to evaluate the effects
	of those interventions on health-related biomedical or behavioral outcomes.

Section 2: Studies subject to FDA jurisdiction

If yes to ANY the study must be registered on Clinicaltrials.gov.

 This is a prospective clinical study of health outcomes in human subjective compares an intervention with an FDA-regulated device against a correst is not a small clinical trial to determine the feasibility of a device, or a small clinical trial to determine the feasibility of a device. 	jects that ontrol. This a clinical
trial to test prototype devices where the primary outcome measure relation feasibility and not to health outcomes.	elates to

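### Envelopes are hand-picked from a set prepared by the enrolling team in an open-label trial, with no random sequence, sealing, ordered use or log described

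*Protocol*

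**What the plan says.** Protocol section 7 (Procedures Involved) describes the design as follows: "This is a non-blinded, randomized, parallel-group study". Allocation takes three sentences. The first has the research team prepare a set of 75 envelopes. The second gives the make-up of that set: "Each will be numbered, 25 will be in propofol group, 25 will be in etomidate group and 25 will be in propofol/etomidate group". The third, and the only one on how a patient is matched to an envelope, reads: "On the day of surgery, one envelope will be randomly picked for each participant".

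Protocol section 17 gives the consent role to the same group: "Research team will obtain consent from interested participants and honor any withdrawal requests based off of randomization group or time-constraints". Section 9 adds: "As this is a minimal risk study, there are no plans to monitor the data".

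The SAP does not mention randomization or concealment.

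**The concern.** Numbered envelopes protect an allocation when they are used in sequence, because a skipped or reused number then shows. Under the stated rule any remaining envelope is a valid draw, so a second pick or a preferred envelope looks the same on paper as an honest one. The protocol calls the pick random but names no device or procedure that makes it so. A person choosing by hand is not a random mechanism.

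There is a plausible motive. Protocol section 3 associates propofol with hypotension and etomidate with steadier haemodynamics. Eligible patients are ASA 2 or 3, so risk varies between them and is visible before induction. Blood pressure change is a primary endpoint. If staff guided frailer patients towards or away from an arm, the groups would differ in the characteristics that drive that endpoint, and enrolling more patients would not correct it.

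**Working it through.** **1. The plan's own figures.** The point concerns procedure and alters no stated number. The protocol's inputs (difference 20 mmHg, SD 25 mmHg, power 0.80, two-sided 0.05 assumed) give n = 2 × [25 × (1.960 + 0.842) / 20]² = 24.53, rounded up to 25. Then 3 × 25 = 75, which matches the envelope count. The SAP's 20 per group with 20% dropout gives 20 / 0.8 = 25.

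**2. What is and is not described.**

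| Element | In the documents |
|---|---|
| Who prepares the envelopes | Research team (protocol 7) |
| Who obtains consent | Research team (protocol 17) |
| Ratio | 25/25/25, numbered (protocol 7) |
| How groups were matched to numbers | Not stated |
| Sealed, opaque | Not stated |
| Order of use | Picked from the set; no order stated |
| Who picks or opens, and whether after consent | Not stated |
| Log of envelope number against participant | Not stated |
| Custodian outside enrolment | Not stated |
| Data monitoring | None planned (protocol 9) |

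The participant numbers in protocol section 11 run from 0001 to 0050. They do not cover 75 envelopes and so do not serve as a link to envelope numbers.

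**3. What one repeat pick does.** With a full set, suppose one unwanted draw is set aside and a second envelope is taken. The chance of the wanted arm rises from 25/75 = 0.333 to 1 − (50/75)(49/74) = 0.559. If the first envelope is returned before the second draw, it is 1 − (2/3)² = 0.556.

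**4. Illustration of the effect on the comparison.** From the SAP, MAP at induction is 80.1 (SD 10.3) for propofol, 90.3 (10.4) for the combination and 91.0 (11.6) for etomidate. Pooled SD = √[(10.3² + 10.4² + 11.6²)/3] = 10.78. Combination minus propofol = 90.3 − 80.1 = 10.2 mmHg. With 20 per group, SE = 10.78 × √(2/20) = 3.41, on 60 − 3 = 57 df.

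The bias is an assumption: 10 to 30% of one arm steered, and those patients' MAP lower by 10 mmHg, giving 0.1 × 10 = 1 to 0.3 × 10 = 3 mmHg. Steering frailer patients away from propofol raises the propofol mean and shrinks the difference. Power is from the noncentral t with noncentrality = difference / 3.41. The last column uses 0.05/3 = 0.0167, on the assumption that the SAP's Bonferroni test covers three pairwise comparisons.

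| Bias (mmHg) | Difference left | Noncentrality | Power at 0.05 | Power at 0.0167 |
|---|---|---|---|---|
| 0 | 10.2 | 2.99 | 0.84 | 0.70 |
| 1 | 9.2 | 2.70 | 0.76 | 0.59 |
| 2 | 8.2 | 2.40 | 0.66 | 0.48 |
| 3 | 7.2 | 2.11 | 0.55 | 0.37 |

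Bias in the other direction exaggerates the difference. If there were no true difference, the same 1, 2 or 3 mmHg would raise the rejection rate from 0.05 to 0.060, 0.089 or 0.139 in an unadjusted test, and from 0.017 to 0.021, 0.036 or 0.063 at 0.0167.

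The arms are fixed at 25, so a patient moved out of one arm enters another. If the swap is between the two arms being compared, both means move and the bias doubles to 2 to 6 mmHg.

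**5. Does the planned analysis absorb it?** In part. If steered patients have a MAP lower by a constant g before and after induction, change from baseline is (post − g) − (pre − g) = post − pre. The gap cancels there and in the time-by-group term. If frailer patients respond differently to the drug, the difference in response remains. Comparisons of MAP level at single time points, which the SAP plans post hoc, stay exposed even to a constant gap.

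**The case against.** The protocol says the pick is random, and drawing from a well-shuffled set of identical sealed envelopes is a legitimate lottery. A reader might infer from the text that staff chose envelopes at will, knew which number held which drug, and could re-pick without trace. The documents support none of these. They permit no choice, mention no key, and do not say that whoever prepared the envelopes also enrolled patients. The set is finite, so a discarded envelope would leave it one short, and the numbers would allow an audit if they were recorded. What stands is that shuffling, sealing and recording are not described, so the safeguards cannot be assumed either.

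Eligibility also narrows the room for steering: surgery is elective, and severe cardiac disease, hypotension and shock are excluded. That limits the likely size of any bias, but variation within ASA 2 and 3 remains.

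A reader might also take the section 17 agreement to "honor any withdrawal requests based off of randomization group or time-constraints" as further evidence of steering. It concerns withdrawal after allocation. That is a separate matter of attrition, and the change proposed here does not address it.

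Finally, a reader might infer that no planned analysis could remove the bias. That is too strong, since a constant baseline gap drops out of change from baseline and of the interaction term.

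**Conclusion.** The point holds as a weakness in the described allocation method. In an open-label trial, envelopes prepared by the team that also obtains consent are picked by hand from the remaining set, and nothing described would prevent or reveal a selective or repeat pick. The documents do not show that this happened, and they give no basis for estimating its size.

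The loss of power from 0.84 to between 0.76 and 0.55 rests on an assumed bias of 1 to 3 mmHg, the SAP's pooled SD, 20 per group and an unadjusted 0.05 test. It shows scale and is not an estimate. A reader might infer that the main risk is a false positive in favour of the combination. Steering frailer patients away from propofol works the other way and shrinks the difference that the trial hopes to show; only the opposite steering would inflate it. This should be changed because the randomized comparison rests on this step and analysis cannot reliably repair it afterwards.

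**What to change.** In protocol section 7, replace the free pick with the following:

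- Match 25/25/25 to envelope numbers 1 to 75 from a computer-generated random list.
- Use sealed opaque envelopes, opened strictly in number order and only after consent.
- Log envelope number, participant, date and time at each opening.
- Have an existing team member who neither enrols nor anaesthetises hold the list.

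The SAP speaks of recruitment in the past tense. If enrolment is complete, report how the envelopes were actually ordered, concealed and logged, including anything that is not known.

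The cost is minor preparation time, a log sheet and a few sentences of protocol text, with no additional patients, staff or drug. One limit remains. Under a fixed 25/25/25 split with open treatment, staff who track past allocations can still guess somewhat better than chance: in a simulation, about 42% of assignments overall and 59% of the last ten, against 33%. Ordered opening and a log stop that guess from being turned into a chosen envelope, but they do not stop it from influencing whom to approach.

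### The repeated-measures analysis has no rule for dosed patients withdrawn for airway difficulty, so a complete-case run would drop them from the primary BP and HR comparison on a post-randomisation event

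*Protocol*

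**What the plan says.** **Loss from analysis.** Protocol section 8 plans 25 randomised per group (75) and expects to complete the analysis on 20 per group (60). It puts the loss down to withdrawal, "due to patient withdrawal either voluntarily or due to formal withdrawal criteria, ie difficulty with securing patient airway". Section 10 adds that the team "can withdraw subjects from the study without their consent if difficulty securing their airway is encountered". Neither section splits the 15 expected losses by reason or arm.

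**Design and timing.** Section 7 states: "This is a non-blinded, randomized, parallel-group study". Pressures and heart rate are recorded "before induction, at induction and intubation followed by 1, 3, 5 and 10 minutes after intubation", which is seven readings. The first primary endpoint in section 6 is "Blood pressure changes during induction"; the second is the same for heart rate.

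**Analysis.** The SAP bases its sample size on MAP at induction (80.1, 90.3 and 91.0 mmHg in groups P, PE and E). It compares haemodynamics with a GLM that has time within subject and group between subjects, checks sphericity with Mauchly's test, and uses Bonferroni post hoc comparisons in SPSS.

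**Populations.** Section 8 names one population, for one purpose: "Demographic variables will be summarized by group for all enrolled subjects". It also promises a disposition summary by group, "including reasons for early withdrawal from the study", and says "All data will be presented in subject data listings". Neither document names the set for the BP and HR comparisons, says whether readings taken before withdrawal are used, or gives a missing-data rule.

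**The concern.** Randomisation makes the three groups comparable at allocation. Removing patients for something that happens after they receive the assigned drug can undo that, and more easily when the person judging airway difficulty knows the drug given. Here the removal also looks unnecessary. In the schedule, induction comes before intubation, so a patient withdrawn because the airway could not be secured would normally already have the before-induction and at-induction readings. Those two bear most directly on the primary endpoints, and the second is the one the SAP is sized on.

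A repeated-measures GLM with Mauchly's test ordinarily needs every time point for every patient, so a patient without the later readings is omitted altogether. If the SAP is run that way, a missing value 10 minutes after intubation removes a valid value at induction. Leaving the set undefined also leaves open who is compared until open-label outcomes have been seen.

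**Working it through.** **1. The plan's own figures.**
- Protocol sample size (difference 20 mmHg, SD 25, power 0.80, two-sided 0.05 assumed): 2 × [25 × (1.960 + 0.842) / 20]² = 24.5, so 25 per group. This reproduces.
- SAP inflation: 20 / (1 − 0.20) = 25. This reproduces.
- SAP omnibus power at 20 per group, with its three means and pooled SD 10.78: 0.887, close to the stated 0.9.
- Expected loss: 75 − 60 = 15, and 15/75 = 20%.

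The SAP budgets for 20 evaluable per group, so power is not the main issue.

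**2. What an airway-withdrawn patient would have.** The readings run: before induction, at induction, intubation, then 1, 3, 5 and 10 minutes after. Loss at the airway stage normally leaves the first 2 of 7. That the difficulty follows dosing is read from this order; the protocol does not say it outright.

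**3. How far a contrast could move.** The documents give no airway counts, so these are assumed: 25 dosed per arm, 2 lost, 23 retained, and loss correlated *r* with induction MAP. SDs are the SAP's (P 10.3, PE 10.4, E 11.6).

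Shift in one arm's retained mean = *r* × SD × (e₁ + e₂)/23, where e₁ = 1.965 and e₂ = 1.524 are the expected two largest of 25 standard normal values. (1.965 + 1.524)/23 = 0.1517.

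| Arm with informative loss | r = 0.3 | r = 0.5 |
|---|---|---|
| P (SD 10.3) | 0.47 | 0.78 |
| PE (SD 10.4) | 0.47 | 0.79 |
| E (SD 11.6) | 0.53 | 0.88 |

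If patients with high MAP are the ones lost, the retained mean falls. PE minus P then moves by about −0.5 to −0.8 mmHg if the loss is informative in PE but not P, and by about +0.5 to +0.8 if only in P. If it is informative in all three arms the shifts cancel: about 0 for PE minus P, and −0.05 to −0.10 for E minus PE. Simulation agrees. If patients with low MAP are lost, the signs reverse.

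**4. Scale.** SE of PE minus P with 23 per arm: √[(10.3² + 10.4²)/23] = √(214.25/23) = 3.05 mmHg (3.27 with 20 per arm). The planned difference is 90.3 − 80.1 = 10.2 mmHg. With a common SD, shift/SE = *r* × 0.1517/√(2/23) = 0.51*r*, or 0.15 to 0.26 of an SE. The SD cancels, so the same ratio would hold for heart rate, for which the documents give no SD.

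**5. Sensitivity.** If only 22 per arm are dosed and 2 are lost, the one-arm shifts are about 0.51 and 0.87 mmHg. A ceiling for one arm with 2 of 25 lost, if the most extreme patients were always the ones lost (normality assumed), is SD × φ(z)/(1 − p) with p = 0.08 and φ(z) = 0.1487: 1.66 (P), 1.68 (PE) and 1.87 (E) mmHg.

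Keeping all dosed patients gives no shift at induction in any of these cases. That is true by construction, because no induction reading is then missing.

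**The case against.** The strongest reply is that the exclusion is not written down. Section 8's 60 is a planning forecast. Section 10 allows withdrawal from the study and is silent on readings already taken. Listwise omission comes from how the software usually behaves, not from the SAP. All of that is right, so the point is an omission with a likely consequence, not a stated rule.

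Second, the protocol promises descriptive summaries of all data, full listings, and withdrawal reasons by group, so a selective loss would be partly visible. That mitigates the gap, but it does not settle who enters the GLM.

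Third, airway losses should be few, because section 4 excludes Mallampati class 4 and BMI of 40 or more. Nothing in the documents suggests that they differ by arm. This also stands.

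Fourth, for the readings after intubation, setting aside patients whose intubation was difficult is a defensible choice of question. That is fair for those times. It is no reason to discard the at-induction reading.

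A reader might also take section 17, which honours withdrawal requests based on randomisation group, as making this point stronger. Those withdrawals would mostly come before dosing, with no post-dose readings to recover. They are a separate limitation that the remedy here does not touch.

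**Conclusion.** The point holds as a cheap improvement. Neither document defines the comparison set, and the SAP's model, run on complete cases, would drop dosed patients from the primary comparison on a post-randomisation event under open allocation, although their induction readings would normally exist.

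A reader might infer that the plan orders these readings to be discarded, or that the trial's result is biased. The documents support neither. They state no deletion rule, do not split the 20% loss, and give no airway rates by arm, so size and direction cannot be determined. Under the assumed losses the shift is about 0.5 to 0.8 mmHg for PE versus P, roughly 0.15 to 0.26 of a standard error and small beside the planned 10.2 mmHg. It is about 0 if loss behaves alike in all arms. The case for change is that the readings should already be in hand and using them costs almost nothing. It does not rest on a large expected bias.

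**What to change.** Define the primary analysis set for BP and HR as all randomised patients who received an induction drug, in their assigned group, using every reading recorded before withdrawal where consent allows. Airway-difficulty patients are included.

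- **Minimum:** if the GLM is kept, also run the at-induction BP and HR contrasts on this set. They need no missing-data model where that reading was recorded.
- **Preferred:** replace the GLM with a mixed model (group, time, group by time) that accepts incomplete time points, with the covariance structure and a fallback stated in advance. An unstructured matrix for seven readings has 7 × 8/2 = 28 parameters on at most 75 patients, so a simpler structure may suit better. Mauchly's test is then not needed.
- Show the analysis without airway-difficulty patients as a sensitivity analysis.
- Report pre-dose withdrawals, including those prompted by allocation, by group in the disposition summary already planned.

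The cost is a few lines in each document and, for the preferred version, a change of model; nothing extra is measured. Two limits remain. Post-intubation contrasts would rely on missing at random, and pre-dose withdrawals stay outside the set. Clinical decisions to withdraw a patient are not questioned, only the use of readings already taken.
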